1. INTRODUCTION

Osteoarthritis (OA) is the most common form of arthritis and causes degenerative structural change that results in pain and decreased mobility. Samumed, LLC is developing SM04690, a small-molecule inhibitor of the Wnt pathway, for the treatment of OA. The purpose of this study is to assess the safety and efficacy of four different strengths of SM04690 administered by intra-articular injection into the target knee joint of moderately to severely symptomatic OA subjects.

2. STUDY OBJECTIVES

2.1. Primary Objective

The primary objective of this study is to determine the effective dose(s) of SM04690 for the treatment of knee OA.

2.2. Secondary Objective

The secondary objective of this study is to evaluate the safety and tolerability of SM04690.

3. STUDY DESIGN

This study is a multicenter, randomized, double-blind, placebo-controlled, parallel-group study of four different concentrations of SM04690 injected into the target knee joint of moderately to severely symptomatic OA subjects.

3.1. Sample Size

A sample size of approximately 630 subjects was randomized at a ratio of 1:1:1:1:1 (0.03 mg active per 2 mL injection : 0.07 mg active per 2 mL injection : 0.15 mg active per 2 mL injection : 0.23 mg active per 2 mL injection : 0.0 mL vehicle : 2.0 mL vehicle). The sample size for this study was based upon accepted dose-finding statistical practice ([Ting et al. 2017](#)).

3.2. Randomization

Subjects were randomized to each treatment group using a permuted block design. Prior to randomization, the presence of unilateral or bilateral knee OA was determined by the investigator and subjects were required to complete the Widespread Pain Index and Symptom Severity (WPI&SS) questionnaire.

The Widespread Pain Index (WPI) is a body map consisting of 19 prespecified areas where subjects can indicate the presence of pain during the past seven days with a possible score 0-19. Question 2 of the Symptom Severity section of the questionnaire (SSQ2) focuses on the presence and severity of three prespecified symptoms (1. fatigue, 2. trouble thinking or remembering, 3. waking up tired) during the past seven days with a possible score of 0-9.

For permuted block randomization, subjects were stratified by knee OA laterality (50% unilateral, 50% bilateral) and WPI&SS score (80% $WPI \leq 4$ and $SSQ2 \leq 2$, 20% $WPI > 4$ and/or $SSQ2 > 2$). A randomization list with a block size of 6 was generated and stored in Medidata Balance. The block size of 6 was selected to accommodate the 6 possible treatment assignments

and limit the possibility of imbalance. Since the study was not stratified by site, predictability with a small block size was not a concern due to competitive enrollment across all sites.

Details on the configuration of Medidata Balance for randomization design and list generation were documented in the Randomization Configuration Plan. The seed used to generate the randomization list was randomly assigned and captured in the Medidata Balance audit trail. The randomization lists and seeds were not accessible to blinded study personnel.

3.3. Study Medication Dosing

SM04690 will be administered in the following dosage strengths:

- SM04690 0.03 mg in 2-mL Injectable Suspension
- SM04690 0.07 mg in 2-mL Injectable Suspension
- SM04690 0.15 mg in 2-mL Injectable Suspension
- SM04690 0.23 mg in 2-mL Injectable Suspension
- SM04690 0 mg; 2 mL vehicle injection only
- SM04690 0 mg; 0 mL sham injection (intra-articular injection procedure is performed identically to all other treatment groups but without the injection of any liquid)

4. STUDY ENDPOINTS

4.1. Primary Endpoints

The primary endpoints of this study include:

1. Evaluate change from baseline OA pain in the target knee as assessed by the weekly averages of daily pain Numeric Rating Scale (Pain NRS) at Week 24
2. Evaluate change from baseline OA pain in the target knee as assessed by Western Ontario and McMaster Universities Osteoarthritis Index (WOMAC) Pain subscore at Week 24
3. Evaluate change from baseline OA function in the target knee as assessed by WOMAC Physical Function (WOMAC Function) subscore at Week 24
4. Evaluate change from baseline in medial joint space width (mJSW) as documented by radiograph of the target knee at Week 24

4.2. Secondary Endpoint

The secondary endpoints of this study include:

1. Evaluate the safety of SM04690 as measured by treatment-emergent adverse events (TEAEs)
2. Evaluate change from baseline OA disease activity as assessed by Patient Global Assessment (PTGA) at Week 24

4.3. Exploratory Endpoints

Additional exploratory endpoints of this study include:

1. Evaluate change from baseline OA pain in the target knee as assessed by WOMAC Pain at Weeks 4, 8, 12, 16, and 20
2. Evaluate change from baseline OA function in the target knee as assessed by WOMAC Function at Weeks 4, 8, 12, 16, and 20
3. Evaluate change from baseline symptoms of OA in the target knee as assessed by WOMAC Total at Weeks 4, 8, 12, 16, 20, and 24
4. Evaluate change from baseline OA pain in the target knee at each week (aside from Week 24) as assessed by Pain NRS
5. Evaluate change from baseline OA disease activity as assessed by PTGA at Weeks 4, 8, 12, 16, and 20
6. Evaluate change from baseline OA function in the target knee as assessed by Knee Injury and Osteoarthritis Outcome Score (KOOS) at Weeks 4, 8, 12, 16, 20, and 24
7. Evaluate change from baseline OA function in the target knee at each week as assessed by KOOS Physical Function Short Form (KOOS-PS)
8. Evaluate change from baseline OA disease activity as assessed by Physician Global Assessment (PGA) at Weeks 4, 12, and 24
9. Evaluate change over time in NSAID usage as assessed by electronic diary responses at every week
10. Evaluate subject perception of study treatment received at Day 1 and Week 24
11. Evaluate outcome differences between treatment with sham and vehicle injections at Weeks 4, 8, 12, 16, 20 and 24

5. STUDY OUTCOME MEASURES

5.1. Safety Outcome Measures

Safety will be assessed by summarizing and evaluating TEAEs, clinical laboratory results, vital signs and concomitant medications.

5.2. Efficacy Outcome Measures

Knee pain was assessed by the subject using Pain NRS. Knee pain and function was assessed by the subject using the WOMAC, KOOS and KOOS-PS questionnaires. Disease activity was assessed by the PTGA and PGA. NSAID usage was assessed by subject self-report of taking an NSAID via electronic diary. The subjects' perception of study treatment was assessed by a paper questionnaire administered immediately after treatment and again at the end of the study. JSW was assessed with radiograph imaging of the target knee.

5.2.1. Pain Numeric Rating Scale

The Pain NRS is an 11-point scale (0-10) for subject self-reporting of average knee pain in the last 24 hours, where 0 represents no pain and 10 represents extreme pain. Subjects were prompted to report average pain in the target knee daily on their electronic device (between 5:00 pm and 11:59 pm) from Screening Visit 2 through the end of the study. An average weekly score (referred to as weekly Pain NRS) was calculated for each subject if they had provided a response for at least 4 out of 7 days in a given week. Weeks are defined as Day -7 through Day -1 (day before treatment) for baseline, Day 1 (day of treatment) through Day 7 for Week 1, Day 8 through Day 14 for Week 2, and so on.

5.2.2. Western Ontario and McMaster Universities Arthritis Index

The WOMAC Version NRS 3.1 instrument is a patient-reported outcome measure to assess the symptoms of OA. Subjects were prompted to complete the WOMAC instrument monthly on their electronic device. The devices required subjects to enter a response for each item before proceeding to the next.

WOMAC consists of 24 questions in three domains: physical function (17 questions), pain (5 questions) and stiffness (2 questions). The response for each question in the NRS format ranges from 0 to 10. Each domain subscore as well as a total score are calculated by adding together the numerical responses for a range of 0 to 240 total points. For analysis, WOMAC Total score as well as all three subscores will be linearly transformed to a 0-100 scale, where 0 represents no difficulty and 100 represents extreme difficulty.

5.2.3. Knee Injury and Osteoarthritis Outcome Score

KOOS is a widely used, non-proprietary tool intended to evaluate pain, symptoms, 2 types of physical function and knee-related quality-of-life. Subjects were prompted to complete the KOOS questionnaire monthly on their electronic device. The devices required subjects to enter a response for each item before proceeding to the next.

Subjects were instructed to answer each item with one of 5 standardized Likert responses. Each item is assigned a score of 0-4 and a normalized score of 0-100 is calculated for each of the 5 subscales (Pain, Symptoms, Activities of Daily Living, Sport and Recreation, Quality of Life) based on the August 2012 scoring instructions ([KOOSscoring2012.pdf](#)). Per these instructions, two composite scores are also calculated: KOOS₅ (the average of all 5 subscales) and KOOS₄ (the average of 4 subscales, excluding ADL). For all subscale and composite scores, 100 represents no difficulty and 0 represents extreme difficulty.

5.2.4. Knee Injury and Osteoarthritis Outcome Score – Short Form

KOOS-PS is a 7-item measure that is used to assess physical function. Subjects were prompted to complete the KOOS-PS questionnaire weekly on their electronic device. The devices required subjects to enter a response for each item before proceeding to the next.

Subjects were instructed to answer each item with one of 5 standardized Likert responses. Each item is assigned a score of 0-4 and a normalized score of 0-100 is calculated. For this study, to align with KOOS, 100 represents no difficulty and 0 represents extreme difficulty.

5.2.5. Patient Global Assessment of Disease Activity

The patient assessment was a 50 mm visual analog scale (VAS) adapted from the Patient Assessment Form © 1999, American College of Rheumatology. Subjects rated how well they were doing, considering all the ways in which illness and health conditions may affect them. The VAS was anchored by “Very Well” (0) on the left and “Very Poorly” (50) on the right. Subjects were prompted to complete the assessment monthly on their electronic device. Scores were subsequently scaled to 0-100.

5.2.6. Physician Global Assessment of Disease Activity

The physician assessment was a 100 mm VAS adapted from the Physician Assessment Form © 1999, American College of Rheumatology. The investigator rated the subject’s disease activity on a paper form on Day 1 and Weeks 4, 12 and 24. The VAS was anchored by “Very Good” (0) on the left and “Very Bad” (100) on the right.

5.2.7. Nonsteroidal Anti-Inflammatory Drug Usage

Subjects were asked “Did you take any medication that is an NSAID in the last 24 hours?” on their electronic device daily (between 5:00 pm and 11:59 pm) from Screening Visit 2 through the end of the study. If a “yes” or “no” response was provided for at least 4 out of 7 days in a given week, a proportion of days with NSAID usage is calculated (days with “yes” response / total number of responses). Weeks are defined as Day -7 through Day -1 for baseline, Day 1 through Day 7 for Week 1, Day 8 through Day 14 for Week 2, and so on.

5.2.8. Evaluation of Success of Blinding

Subjects were prompted, “Please indicate which treatment arm you believe you were assigned to for this study” on a paper form on Day 1 (post-injection) and on Week 24. The form captured responses of “Study drug injection,” “Injection of 2 mL inactive vehicle substance,” “Needle insertion into the knee with no vehicle substance injected” and “Do not know”.

5.2.9. Joint Space Width

Radiograph of the knee joints was taken at Screening Visit 1 and Week 24. Whenever possible, the radiographs obtained the posterior-anterior (PA) view according to the Image Review Charter. Medial and lateral JSW measurements of the target knee were provided by the vendor, Medical Metrics, Inc. (MMI).

6. ANALYSIS DATASETS

6.1. Full Analysis Set

The Full Analysis Set (FAS) includes all subjects who were randomized and received a study injection.

6.2. Modified Full Analysis Set

The Modified Full Analysis Set (mFAS) includes FAS subjects who received a protocol-specified injection. Subjects who were administered a treatment that is not prescribed by the protocol are excluded from this analysis set.

6.3. Per-Protocol Analysis Set

The Per-Protocol Analysis Set (PPAS) includes mFAS subjects who completed the study and did not have any major protocol deviations (see Section 11).

6.4. Safety Analysis Set

The Safety Analysis Set (SAS) includes all subjects who received a study injection.

7. EFFICACY ANALYSIS

7.1. General Considerations

Unless otherwise specified, efficacy analyses will be performed on the FAS, mFAS and PPAS. For continuous variables within each treatment group, the outcome measure at each visit, as well as absolute change (outcome – baseline), will be summarized using descriptive statistics (number of subjects, mean, standard deviation, median, minimum and maximum). Categorical variables will be summarized with frequency tables.

Since this study was stratified based upon known clinical phenotypes of OA, all efficacy analyses will be completed in three subject populations: 1) subjects with unilateral symptomatic OA, 2) subjects with unilateral symptomatic OA and without widespread pain ($WPI \leq 4$ and $SSQ2 \leq 2$), and 3) all subjects.

Subject-level listings will be provided for each outcome measure.

7.2. ANCOVA Model for Continuous Efficacy Outcomes

ANCOVA models will be used for all continuous efficacy outcome measures summarized by change from baseline in order to test the following four hypotheses:

$$H_0: (\beta_i - \beta_0) = 0$$

$$H_A: (\beta_i - \beta_0) \neq 0, \text{ where } i = 1,2,3,4$$

In the statement above, β is the least squares estimate in the change in the continuous efficacy outcome from baseline at each timepoint (where β_0 is the estimate for vehicle), and i represents each of the four SM04690 treatment groups.

Least squares estimate of difference between each treatment group and placebo in the change in the continuous efficacy outcome from baseline at each timepoint, adjusted for baseline value, will be reported along with unadjusted 95% confidence intervals and P values.

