A phase 3, long-term extension study (SM04690-OA-05) is also being performed to monitor the long-term safety, tolerability, and efficacy of treatment of SM04690 or placebo previously injected in the target knee joints of subjects with moderately to severely symptomatic OA from a Samumed-sponsored SM04690-OA phase 2 or phase 3 study. This study is a multicenter, observational study in subjects that have previously been treated with SM04690 or placebo injected into the target knee joint. Approximately 2000 subjects will be consented and will participate in a 60 month follow-up period. Clinic visits are scheduled at Months 6, 12, 24, 36, 48, and 60 [End of study (EOS)]/Early Termination (ET).

This phase 2 study, SM04690-OA-04, is a placebo-controlled, double-blind, parallel group study of four concentrations of SM04690 (0.03, 0.07, 0.15, and 0.23 mg per 2 mL injection) injected into the target knee joint of subjects with moderately to severely symptomatic OA. Based upon the interim data analysis of SM04690-OA-02, key phenotypes of laterality (unilateral vs bilateral) as well as chronic pain (as measured by the Widespread Pain Index) were identified as confounding variables impacting the overall assessment of both radiologic and clinical efficacy outcomes. The design of SM04690-OA-04 is based upon the SM04690-OA-02 design while assessing strategies to combat the confounding impact of laterality and chronic pain.

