10.6 MEASURES TO MINIMIZE BIAS

10.6.1 BLINDING PROCEDURES

This is a double-blind study. Study medication will be provided to the investigational center. The investigational center must identify unblinded personnel who will be responsible for preparing the appropriate dilution of the study medication and who are able to perform the injection of study medication and/or vehicle. Study personnel administering or preparing study medication and reference therapy must minimize any contact with the subject following the injection and may not perform any study assessments throughout the duration of the study. Each site will be required to document a blinding plan that identifies the blinded and unblinded personnel at the investigational center and describes how the study blind will be maintained.

Subjects will be assigned a subject number at their Screening Visit 1. On Day 1, eligible subjects will be randomized via the Medidata database. Upon randomization of a subject, a Treatment Arm Notification email will be sent from [contact] to the unblinded investigational staff member designated in the Site-Specific Blinding Plan. Subjects will be randomized 1:1:1:1:1:1 (0.03 mg active per 2 mL injection : 0.07 mg active per 2 mL injection : 0.15 mg active per 2 mL injection : 0.23 mg active per 2 mL injection : 0.0 mL vehicle : 2.0 mL vehicle) to each treatment group using a permuted block design stratified by presence of bilateral knee OA (50% bilateral, 50% unilateral) and WPI&SS (80% $WPI \leq 4$ and $SSQ2 \leq 2$, 20% $WPI > 4$ and/or $SSQ2 > 2$). Specific information regarding the use of Medidata Balance to store and implement the permuted block design will be detailed within the SAP.

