7.5.2. Mixed-Effects Model for Repeated Measures

Change over time in primary and secondary endpoints (weekly Pain NRS, WOMAC Pain, WOMAC Function and PTGA) as well as weekly measures (KOOS-PS and NSAID usage) will be characterized using mixed-effects models for repeated measures (MMRM). The models will estimate change from baseline with treatment, week, treatment×week interaction and baseline value as covariates.

For weekly measured outcomes, MMRM will be estimated assuming a Toeplitz variance-covariance matrix. The Toeplitz structure is a more generalized form of autogressive-1 (AR1) structure, allowing the data to inform how the correlation between within-subject observations decreases over time instead of implicitly defining a uniform decay structure. For monthly measured outcomes, MMRM will be estimated assuming an unstructured variance-covariance matrix, allowing the data to fully inform the correlation between within-subject observations. (Kincaid 2005)

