7.5.4. Comparison of Vehicle and Sham

The change from baseline in weekly Pain NRS, WOMAC Pain, WOMAC Function and PTGA at Weeks 4, 8, 12, 16, 20 and 24, as well as mJSW at Week 24 will be analyzed with an ANCOVA model with the following hypothesis:

$$H_0: (\beta_{\text{vehicle}} - \beta_{\text{sham}}) = 0 ; H_A: (\beta_{\text{vehicle}} - \beta_{\text{sham}}) \neq 0$$

Least squares estimate of difference between vehicle and sham in the change in outcome from baseline, adjusted for baseline value, will be reported along with unadjusted 95% confidence intervals and P values.

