7.5.5. Subgroup Analysis

Efficacy analyses described in Sections 7.3 and 7.4 will be further analyzed by additional, complementary clinical phenotypes of OA not already defined in Section 7.1.

The additional clinical phenotypes of OA include:

1. Bilateral Symptomatic OA
2. $WPI \leq 4$ and $SSQ2 \leq 2$
3. $WPI > 4$ and/or $SSQ2 > 2$
4. Unilateral Symptomatic OA with $WPI > 4$ and/or $SSQ2 > 2$
5. Bilateral Symptomatic OA with $WPI \leq 4$ and $SSQ2 \leq 2$

6. Bilateral Symptomatic OA with WPI > 4 and/or SSQ2 > 2

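### The ANCOVA, the vehicle–sham ANCOVA and the MMRM omit the randomisation strata, so if the strata are prognostic the reported standard errors are on average too large wherever strata are pooled

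*SAP*

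**What the plan says.** **Design.** SAP 3.2: "For permuted block randomization, subjects were stratified by knee OA laterality (50% unilateral, 50% bilateral) and WPI&SS score", the latter split 80/20, with blocks of 6. Protocol 10.6.1 agrees: "using a permuted block design stratified by presence of bilateral knee OA (50% bilateral, 50% unilateral) and WPI&SS". Protocol 2.2 gives the reason. In the earlier phase 2 study, laterality and chronic pain "were identified as confounding variables impacting the overall assessment of both radiologic and clinical efficacy outcomes".

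**Models.**
- SAP 7.2 (ANCOVA) states that dose–vehicle differences in change of each "continuous efficacy outcome from baseline at each timepoint, adjusted for baseline value, will be reported along with unadjusted 95% confidence intervals and P values". Sections 7.3, 7.4 and 7.5.1 use this model, as do the MCP-Mod input (7.6) and the LOCF analysis (9.4). Protocol 10.4.2, 10.4.3 and 10.4.7 name the same single covariate.
- SAP 7.5.4 (vehicle against sham): "Least squares estimate of difference between vehicle and sham in the change in outcome from baseline, adjusted for baseline value".
- SAP 7.5.2 (MMRM): "The models will estimate change from baseline with treatment, week, treatment×week interaction and baseline value as covariates".

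**Use of the strata.** They define analysis populations (SAP 7.1: "Since this study was stratified based upon known clinical phenotypes of OA, all efficacy analyses will be completed in three subject populations") and six further subgroups (SAP 7.5.5: efficacy analyses "will be further analyzed by additional, complementary clinical phenotypes of OA not already defined in Section 7.1"). They enter no model.

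**The concern.** Stratified blocking makes the arms nearly equal in stratum mix, so differences between strata largely cancel out of the treatment contrast. A model without the strata does not know this. It counts variation between strata as residual noise, and its standard error describes a less precise design than the one that was run.

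If the strata are prognostic beyond baseline value, confidence intervals in the pooled populations are on average wider, and tests more conservative, than the design supports. MCP-Mod inherits this through its ANCOVA input. The sponsor chose these factors because they mattered in the earlier study, so leaving them out of the models gives up part of what stratifying achieved.

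**Working it through.** **Inputs**
- About 630 subjects, equal allocation to six arms, about 105 per arm (Protocol 10.5).
- Stratum mix 50/50 by 80/20 (SAP 3.2), so 630 × 0.5 × 0.8 = 252 and 630 × 0.5 × 0.2 = 63 per stratum, each twice. The caps of 240, 240, 60 and 60 in Protocol 7.3.2 have the same proportions.
- Stratum effect: not given. Let *d* be the difference between the two levels of a factor, in residual SDs after baseline adjustment. Assumed values: 0, 0.2, 0.3, 0.5.
- Two-sided 5%, implied by the 95% intervals. The 80% power is only a benchmark. The plan states no power, effect size or SD, so it has no figure of its own to reproduce here.

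**Step 1. Where strata are pooled.** All subjects (four strata), unilateral subjects (two), and three subgroups of SAP 7.5.5: bilateral, WPI≤4 and SSQ2≤2, and WPI>4 and/or SSQ2>2. Unilateral subjects without widespread pain and the other three subgroups are single strata, so their excess is zero.

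**Step 2. Standard error.** A two-level factor with shares p and 1−p adds p(1−p)d² to a residual variance of 1. That is 0.5 × 0.5 × d² = 0.25d² for laterality and 0.8 × 0.2 × d² = 0.16d² for WPI&SS. With v the sum that applies, the SE ratio without to with stratum is √(1+v). Example, all subjects, both factors, d = 0.5: v = 0.41 × 0.25 = 0.1025 and √1.1025 = 1.050.

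| Setting | v | SE excess, d = 0 / 0.2 / 0.3 / 0.5 |
|---|---|---|
| All subjects, both factors | 0.41d² | 0 / 0.8 / 1.8 / 5.0% |
| All subjects, laterality only | 0.25d² | 0 / 0.5 / 1.1 / 3.1% |
| All subjects, WPI&SS only | 0.16d² | 0 / 0.3 / 0.7 / 2.0% |
| All subjects, WPI&SS effect only in unilateral | 0.1d² − (0.1d)² = 0.09d² | 0 / 0.2 / 0.4 / 1.1% |
| Unilateral, or bilateral subgroup | 0.16d² | 0 / 0.3 / 0.7 / 2.0% |
| Subgroups pooled over laterality | 0.25d² | 0 / 0.5 / 1.1 / 3.1% |

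Which of all subjects and unilateral subjects loses more depends on the unknown effects (compare rows 1, 3 and 4 with row 5).

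**Step 3. Power.** Where the adjusted model has 80%, power = Φ(2.8016 − 1.95996√(1+v)). All subjects, both factors: 80 / 79.5 / 79.0 / 77.1%. Unilateral: 80 / 79.8 / 79.6 / 78.9%.

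**Step 4. ANCOVA simulation** (3,000 null trials, four dose–vehicle tests each, blocks of 6, strata as above). Reported-SE ratios were 1.000 / 1.008 / 1.019 / 1.051 in all subjects and 1.000 / 1.003 / 1.007 / 1.020 in unilateral subjects, matching the formula.

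A second set of 6,000 trials per scenario, with 10% of outcomes missing at random (an assumption), was indexed by R² = v/(1+v), the share of variance the strata explain. For d = 0.5 this is 0.1025/1.1025 = 9.3%. At R² = 10%:
- The true SD of the estimate was almost the same without and with the stratum term (0.1402 and 0.1394).
- The mean reported SE fell from 0.1458 to 0.1383 when the term was added.
- With unstratified randomisation, the unadjusted model's SE matched the true SD (0.1456/0.1462 = 1.00). The excess therefore comes from ignoring the stratification.
- For vehicle against sham, reported SE over true SD was 1.03, with type I error 3.9%.

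For R² of 0 / 2 / 5 / 10 / 20%, type I error without the term was 4.8 / 4.5 / 4.2 / 4.4 / 3.2%, and bias was about zero.

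**Step 5. MMRM** (monthly, unstructured, complete data, assumed within-subject correlation 0.6). Week 24 SE excess without stratum against stratum × week, d = 0.2 / 0.3 / 0.5: all subjects 0.8 / 1.8 / 5.1%, unilateral 0.3 / 0.7 / 2.0%. If the stratum effect rises linearly to d at Week 24, a stratum main effect alone still leaves 0.2 / 0.4 / 1.0% in all subjects. In the weekly Toeplitz model a constant stratum effect adds v to every covariance entry, so with complete data the ratio is again √(1+v). A time-varying effect was not computed there.

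**Step 6. Single results.** Adjustment also moves the estimate. Among null comparisons with complete data, the stratum-adjusted P value was the larger one in 53 / 37 / 32 / 23% (all subjects) and 58 / 48 / 41 / 34% (unilateral) for d = 0 / 0.2 / 0.3 / 0.5.

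**The case against.** The loss may be zero. Protocol 2.2 gives no size, and its wording could mean effect modification, which a stratum main effect does not address. The plan handles phenotype deliberately, through separate populations and subgroups. The entry criteria (non-target knee score below 4, target knee as the main source of pain, fibromyalgia excluded) may narrow the contrast between strata. Protocol 10.2 states that no formal hypothesis is tested, no power is claimed, and no documented decision rule changes. The precision of the estimate is hardly affected; only its reported SE is.

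Most of this stands as a limit on size. It does not remove the point: analysing populations separately leaves stratum variation in the residual of every population that pools strata, including all subjects.

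Two objections to the remedy also stand. Changing the protocol text would require an IRB-approved amendment, and Protocol 10.1 leaves the full description to the SAP. The gain from stratum × week in weekly models was not computed for a time-varying effect. Moreover, in one simulation with variance rising over the weeks, the Toeplitz Week 24 SE was too small without and with the strata (0.89 and 0.84 of the true SD). That is a separate problem with the covariance structure, which adding strata does not cure.

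**Conclusion.** The concern holds. No efficacy model contains the factors by which subjects were randomised. If those factors predict change beyond baseline value, model-based standard errors are on average too large wherever strata are pooled. For assumed effects up to 0.5 residual SD per factor, the ANCOVA excess is at most 5.0% in all subjects and 2.0% in unilateral subjects, or 2.9 and 1.1 points off an illustrative 80% power. A larger effect would cost more: R² = 20% gives 1/√0.8 = 1.118, about 12%, and in simulation power at an assumed 0.4 SD difference was 79.7% without the stratum term and 86.4% with it. If the strata are not prognostic, nothing is lost.

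This is not a validity error. With complete data or data missing at random, the omission causes no bias and no excess false positives, and a single P value can move either way. The change should be made because it costs almost nothing, not because the planned results would be wrong.

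**What to change.** Add to SAP 7.2: *The model will also include randomisation stratum, as recorded at randomisation, as a fixed effect: the four-level laterality × WPI&SS stratum in all subjects, and WPI&SS group in unilateral subjects. No stratum term is used in unilateral subjects without widespread pain. Arm-level LS means will use observed stratum margins.*

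Then:
- Make the same addition in 7.5.4 and in the ANCOVA input to 7.6. The LOCF ANCOVA in 9.4 follows.
- In 7.5.2 add stratum and stratum × week. The evidence for the interaction is from the monthly models.
- In the 7.5.5 subgroups include whichever factor still varies.
- Align Protocol 10.4.2, 10.4.3 and 10.4.7 if the protocol is amended for other reasons. The SAP can carry the detail alone.

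Observed margins matter only for arm-level means. Equal weighting would describe a 50/50 widespread-pain mix instead of 80/20, a shift of (0.5 − 0.2)d = 0.3d, or 0.06 / 0.09 / 0.15 SD for d = 0.2 / 0.3 / 0.5. Differences between arms do not change.

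**Cost.** No new data. The ANCOVA uses at most 3 df in all subjects and 1 in unilateral subjects. In the MMRM, stratum with stratum × week takes 3 parameters per time point in all subjects (3 × 6 = 18 monthly, 3 × 24 = 72 weekly) and 1 per time point in unilateral subjects. Protocol 10.1 has the SAP finalised before database lock, but the documents give no lock date. If lock has passed, report the stratum-adjusted models as a labelled sensitivity analysis.
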